## **5.2. Full Analysis Set (FAS) or the Overall Safety Population (OSP)**

The Full Analysis Set (FAS) or the OSP includes every subject who received at least one dose of any study drug recorded in the Data Management (DM) database excluding screen failures.

- The data analysis for Adverse Events or other Safety variables will be performed on the OSP.
- In the event, the phase II component of the study is implemented and a prespecified null hypothesis comparing study treatment in DIPG subjects with either historical control assumptions or an external control is likely, the primary analysis of OS will be based on the OSP population.

## **5.3. Per Protocol (PP) Population or the Evaluable Safety Population (ESP)**

The PP population is defined as the ESP. The ESP is a subset of the FAS.

- The ESP includes subjects who received Ad-RTS-hIL-12 + at least one dose of their cohort-specific dose of veledimex.
- The ESP are also subjects who have not had a major protocol deviation for which the key efficacy endpoints could be regarded as confounded or uninterpretable.
- Subjects who have had minor protocol deviation(s) that are thought not to impact efficacy will be included in this analysis population.

The ESP will be used for

- Making decisions regarding escalation to higher veledimex doses for Arms 2 cohorts, based on a standard 3 + 3 design.
- Any tables, figures, or listings for dose recommendation and DLT evaluation by the SRC
- In the event, the phase II component of the study is implemented, the secondary analysis of the overall OS hazard rate, the OS at prespecified timepoints, PFS and the ORR will be based on the ESP population.

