14. ASSESSMENT OF SAFETY

Safety will be evaluated in the Overall Safety Population (OSP) and the Evaluable Safety Population (ESP) using CTCAE v5.0.

The OSP includes all subjects who received at least 1 dose of veledimex or Ad-RTS-hIL-12.

The ESP includes all subjects who received Ad-RTS-hIL-12 and at least one dose of veledimex after Ad-RTS-hIL-12 administration, and are BSA conformant.

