16. STATISTICAL METHODS

This study is designed as a multicenter Phase I/II dose escalation study in pediatric subjects with brain tumors. Enrollment in Arm 1 Cohort 1 is open to subjects except those with DIPG; enrollment in Arm 2 (*i.e.*, Cohorts 3 and 4) is open to subjects with DIPG only. Cohorts will be enrolled according to a standard 3 + 3 design (see [Section 7.1](#)).

The primary analysis will be performed after all subjects complete the Initial Follow-up Period (Day 56). Additional analyses will be performed to determine ORR, PFS, and OS. The final analysis will be performed when the last subject completes two years of follow-up.

A formal statistical plan for the analysis and presentation of data from this study will be prepared prior to database lock. Deviations from the statistical analyses outlined in this protocol will be indicated in this plan; any further modifications will be noted in the final clinical study report.

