16.1. Populations for Analysis

This is an amendment to an ongoing study that has been previously described. For all practical purposes the connotation of the safety population for the planned safety analysis are subjects being denoted in defining the overall safety population (OSP) defined below to distinguish this group from the subgroup of subjects denoted as the evaluable safety population (ESP) who must receive Ad-RTS-hIL-12 and at least one dose of veledimex after injection.

This distinction provides for inclusion of both drug components (Ad-RTS-hIL-12+ veledimex) in order to evaluate dose escalation via the rule-based criteria fundamental to the 3+3 method. This means that during dose escalation if at least one of three Ad-RTS-hIL-12 treated subjects does not receive at least one dose of veledimex, additional eligible subjects will be enrolled as applicable in order to achieve the samples size of three evaluable subjects to assist the SRC's evaluation when making a dose escalation or a dose de-escalation decision. Specifically,

- The OSP will be used to perform safety evaluations for all subjects who have received at least one dose of veledimex or Ad-RTS-hIL-12.
- The ESP will include subjects who received Ad-RTS-hIL-12 and at least one dose of their cohort specific-dose of veledimex after Ad-RTS-hIL-12 administration and are BSA conformant. The ESP will be used to make decisions regarding escalation to higher veledimex doses for Arms 1 and 2 separately, based on a standard 3 + 3 design, as described in [Section 7.3](#).
- The Pharmacokinetics Population (PKP) for veledimex includes all subjects who receive veledimex with sufficient PK timepoints.

Up to 30 evaluable subjects in the Phase II expansion cohort may be enrolled to provide time to OS estimation. This subgroup will include subjects treated with both Ad-RTS-hIL-12 and at least one dose of veledimex as defined by the ESP and other evaluability criteria described in the Statistical Analysis Plan.

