## **8. PROTOCOL DEVIATIONS**

A protocol deviation is any change, divergence, or departure from the study design or procedures defined in the protocol.

- Important protocol deviations are a subset of protocol deviations that may significantly impact the completeness, accuracy, and/or reliability of the study data or that may significantly affect a subject's rights, safety, or well-being.
- Where applicable, important protocol deviations will be categorized as major protocol deviations.
  - Protocol deviations that are not deemed important protocol deviations are classified as minor protocol deviations
- The list of protocol deviations along with whether the deviation is classified as major or minor will be finalized prior to database lock.

No subject will be removed from any analysis population because of a protocol deviation.

In accordance with ICH E3, subject eligibility violations and important post- treatment protocol deviations will be identified and listed by subject ID and study center. Major deviations that are considered to potentially impact the efficacy or safety analyses will be tabulated. Important protocol deviations will be identified prior to database lock. Protocol deviations will be listed and summarized by type.

- Deviation from inclusion/exclusion criteria
- Withdrawal criteria met during the study but subject ID was not withdrawn
- Prohibited concomitant medications
- Treatment deviation
- Other protocol deviation

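### SAP 5.3 redefines the ESP used for DLT reporting: it drops BSA conformance and adds a deviation exclusion that SAP 8 forbids

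*SAP*

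**What the plan says.** The protocol defines the ESP in the synopsis, in Section 14 and in Section 16.1. Besides the vector, Section 14 requires "at least one dose of veledimex after Ad-RTS-hIL-12 administration, and are BSA conformant". Section 16.1 requires "at least one dose of their cohort specific-dose of veledimex after Ad-RTS-hIL-12 administration and are BSA conformant". None of the three has a protocol-deviation criterion.

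SAP 5.3 equates the ESP with a per-protocol population. Besides the vector it asks for "at least one dose of their cohort-specific dose of veledimex", and it restricts the set to "subjects who have not had a major protocol deviation for which the key efficacy endpoints could be regarded as confounded or uninterpretable". Subjects with minor deviations stay in. The same section assigns the ESP to Arm 2 escalation decisions and to SRC outputs on dose and DLTs. SAP 4.4 uses it for the recommended Phase II dose. SAP 11 uses it for the DLT listings and, if applicable, the DLT proportions.

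SAP 8 states: "No subject will be removed from any analysis population because of a protocol deviation". It adds that the list of deviations "along with whether the deviation is classified as major or minor will be finalized prior to database lock".

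Protocol 16 says of the SAP: "Deviations from the statistical analyses outlined in this protocol will be indicated in this plan". SAP 6.1, which lists changes from the planned analysis, does not mention a new ESP definition.

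**The concern.** DLT occurrence by cohort is part of the primary endpoint (Protocol 16.3.1, SAP 4.1.1), and the ESP is the set on which it is reported. Whether an efficacy endpoint can be interpreted is not a sensible test for membership of a toxicity denominator. As written, two programmers could build different ESPs from the same SAP: one following 5.3 and dropping a subject, the other following 8 and keeping that subject. The choice could be made at database lock with the DLT data in view.

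The BSA omission works in the other direction. Protocol 7.1 allows some subjects without a matching BSA dose to be enrolled, but says they do not count toward the recommended dose and are analyzed separately. SAP 5.3 has no condition that keeps them out of the reported ESP.

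**Working it through.** No figure in the documents depends on the ESP definition, so there is none to reproduce. The check compares the texts and then illustrates the effect.

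**Step 1: the definitions side by side.**

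| Condition | Protocol (synopsis, 14, 16.1) | SAP 5.3 | Effect in Arm 2 |
|---|---|---|---|
| Received vector | yes | yes | none |
| Veledimex dose after vector | yes | order not stated | none: Arm 2 veledimex starts on Day 1 (Protocol 10.2) |
| Cohort-specific dose | yes, in 16.1 | yes | none |
| BSA conformant | yes | absent | non-conformant subjects can enter |
| No efficacy-confounding major deviation | absent | yes | conformant subjects can be dropped |

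Two differences therefore matter for Arm 2. The cohort-specific dose does not stand in for BSA conformance, because Protocol 16.1 lists both.

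**Step 2: SAP 5.3 against SAP 8.** The ESP is one of the analysis populations in SAP Section 5. Section 5.3 keeps a subject out because of a deviation. Section 8 rules that out for any analysis population and names no exception.

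**Step 3: was the change delegated or declared?** Protocol 16.1 describes the Phase II subgroup for OS estimation "as defined by the ESP and other evaluability criteria described in the Statistical Analysis Plan". That lets the SAP add criteria to the ESP for that subgroup. It does not let the SAP redefine the ESP used for DLTs. The declaration that Protocol 16 requires is missing from SAP 6.1.

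**Step 4: timing.** Under Protocol 7.3 the SRC meets once the last subject of a cohort has completed the 28-day DLT window. The major or minor class of a deviation need only be final by database lock. The reported set can therefore change after the SRC has reviewed the cohort.

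**Step 5: illustration.** Inputs: cohorts of 3 to 6 (synopsis, Sample Size Determination) and the line at 33% or more with DLTs (Protocol 7.5, SAP 4.4). Assumption: one subject leaves or enters; the documents give no deviation rate. Let d be subjects with a DLT and n the ESP size.

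- A subject with a DLT is excluded, (d − 1)/(n − 1): 2/6 = 33.3% becomes 1/5 = 20.0%, and 2/5 = 40.0% becomes 1/4 = 25.0%. Both cross the 33% line. 2/4 = 50.0% becomes 1/3 = 33.3%, and 2/3 = 66.7% becomes 1/2 = 50.0%; neither crosses.
- A subject without a DLT is excluded, d/(n − 1): 2/6 = 33.3% becomes 2/5 = 40.0%, and 1/6 = 16.7% becomes 1/5 = 20.0%.
- A BSA non-conformant subject with a DLT enters after SRC review, (d + 1)/(n + 1): 0/3 becomes 1/4 = 25.0%.

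Under the protocol definition, with SAP 8 applied, none of these changes occurs.

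**The case against.** SAP 5.3 can be read as an entry condition and SAP 8 as a bar on later removal. That reading is possible, and one exception clause would settle the conflict. But Section 8 covers every population without exception, so the reader has to supply the clause.

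The DLT percentages may never be printed. SAP 6.1 prefers listings to summaries of very small samples, and SAP 11 gives the proportion only if applicable. This stands, and Step 5 is no more than an illustration. The DLT listing is itself on the ESP, however, so an excluded subject would be missing from it.

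On BSA, Protocol 7.1 allows dosing of non-conformant subjects only after SRC review of the cohort, and SAP 13.2.2 classes BSA-adjusted dosing as below 75%, 75% to 125% and above 125%. These subjects are therefore outside the set under review and can be identified. That does not supply the missing ESP condition.

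Three stronger readings are tempting and are not supported:

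- A reader might infer that escalation decisions would change, since SAP 5.3 names the ESP for them. The protocol's rules (7.3, Table 5) work on counts of subjects with DLTs. The SRC meets after the 28-day window, and deviations need not be classified by then. Its decisions need not change. Nor are events hidden, because SAP 13.1 lists adverse events for all subjects in the OSP.
- A reader might infer a breach of the minimum of three ESP subjects (Protocol 16.4.2) when 0/3 becomes 0/2. That minimum would already have been met at SRC review; a later reclassification changes only a reported n.
- A reader might count the unstated dose order and the per-protocol label as further live defects. The order matters only in Arm 1, where a dose precedes the vector. That arm has three subjects, is concluded, and its database was locked on 08-Nov-2019 (SAP 2.1.1). The label and the exclusion are one difference.

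**Conclusion.** The point holds. SAP 5.3 changes the ESP for DLT and dose outputs in two ways that matter for Arm 2, without declaring it, and one of the two contradicts SAP 8. The consequence is limited to reporting. A subject could drop out of the ESP DLT listing, and out of the DLT proportion if one is given, after the SRC has reviewed the cohort. A BSA non-conformant subject could enter it. The 2/6 to 1/5 shift rests on one assumed exclusion of a subject with a DLT; how likely that is cannot be judged from the documents. It should be fixed before database lock. It gives no ground for doubting the SRC's decisions.

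**What to change.** - **SAP 5.3:** restore the Protocol 16.1 definition of the ESP for DLT and dose outputs, and remove the major- and minor-deviation bullets from it. State that BSA conformance is judged against the 75% to 125% limits of the protocol dosing table. Table 4b has rows outside those limits. Some carry footnote b and some do not, while footnote a says the dose is within 25% of target. The sponsor must reconcile those rows and footnotes.
- **Efficacy set:** put any deviation-based evaluability criteria in a separately named set. It may serve the Phase II OS subgroup, as Protocol 16.1 allows. It should not be used for DLT or dose outputs.
- **SAP 8:** name the ESP entry conditions and that efficacy set as the only exceptions. The first is needed because off-target BSA is itself exclusion criterion 3 (Protocol 8.2).
- **SAP 11:** state that DLT outputs use the restored ESP and that BSA non-conformant subjects are tabulated separately.
- **SAP 6.1:** record the change.

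The cost is SAP wording in five places, plus the sponsor's reconciliation of the dosing table. The ESP change uses the protocol definition as it stands, so it needs no additional subjects or visits.

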## **5.4. Pharmacokinetics Population (PKP)**

The PKP includes all subjects who receive veledimex with sufficient PK time points. All Pharmacokinetics analyses will be based on the PKP.

## 6. PLANNED ANALYSES

### 6.1. Changes from Planned Analysis

The major change to the original planned analyses is that for all practical purposes, statistical summaries of very small sample sizes will be avoided. Instead, relevant data listings by subject for the OSP and ESP will be presented along with descriptions of subject characteristics as applicable.

When Amendment 2 was implemented,

- Arm 2 enrollment was opened, using the nowEDC database.
- The data for Arm 1, Cohort 1, consisting of 3 subjects for whom the data were captured in Rave eCRF will be summarized separately from the data captured based on DIPG eligibility, beginning with Arm 2, cohort 3.
- After completion of enrollment of DIPG subjects in cohort 3 and cohort 4, the data from the Arm 1, cohort 1, may be combined for reporting purposes in which case remapping the data on the three subjects for whom the data are complete will be applied to creating derived variables like those to be chosen when data extractions from the nowEDC are implemented
- Therefore, this current version of the SAP for ATI001-103 based on amendment 2 will not include tables shell entries for Arm 1, Cohort 1.

### Interim Analyses

There is no formal interim analysis planned for this study.

- There will be SRC meetings to evaluate the subjects' safety data.
- The SRC will determine whether the dosing at the specified level (10 mg or 20 mg) is appropriate for escalation or as the recommended Phase 2 pediatric dose.
- After the completion of phase I dose escalation of Arm 2, the SRC may recommend expanding the current study for one of the doses evaluated in either cohort 3 or 4 in which case a cohort expansion of up to 30 to 35 evaluable DIPG subjects will be enrolled.
- This new cohort of subjects will be defined and referenced as the Phase II component of the study.

### Final Analyses and Reporting

All final planned analyses per protocol and this SAP will be performed only after database lock.

## 7. GENERAL STATISTICAL ANALYSIS CONSIDERATIONS

All analyses described in this plan are considered priori analyses in that they have been defined prior to locking the database. All other analyses, if any, designed subsequently to locking the database, will be considered post hoc analyses and will be described as exploratory analyses in the Clinical Study Report.

For this study,

- Multiplicity adjustment will NOT be performed for analysis.
- Possible covariate effects will NOT be adjusted for analysis.
- No imputations for missing or partial data will be made.
- Data across multiple study sites will be pooled for an integrated summary.
- SAS version 9.4 or higher will be utilized for all listings and tables.

## 7.1. General Statistical Procedure

The descriptive statistics for continuous variables (e.g., age) will be the number of subjects with a non-missing value of the variable (n), mean, standard deviation (SD), median, quartiles (Q1, Q3), minimum and maximum. Mean, median, Q1, and Q3 will be reported to 1 more decimal place than the raw data. The SD will be reported to 2 more decimal places than the raw data. Minimum and maximum will be reported the same as the original data.

In addition to the above descriptive statistics, coefficient of variation (CV%), geometric mean and geometric CV% will also be used to summarize the drug veledimex concentration where applicable.

Coefficient of variation CV% is calculated as  $100 \times (\text{SD}/\text{mean})$ . Geometric CV% is calculated as follows:  $\text{CV\%} = 100 \times \sqrt{\exp(\hat{\sigma}^2) - 1}$ , where  $\hat{\sigma}^2$  denotes the estimated variance of the log-transformed values.

Categorical variables will be summarized by frequency table which includes the number of subjects with a response in the category and the percentage of the total number of subjects in that particular column. Unless otherwise stated, missing responses will NOT be included in the analysis. Percentages will be rounded to one decimal place.

Unless otherwise stated, data will be tabulated by arm and dose cohort, and overall according to the defined population. If dose escalation is stopped before reaching higher veledimex doses, those columns will be omitted from the summaries.

All listings will be ordered by arm and dose cohort, and subject ID for available data.

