The starting dose in Cohort 1 will be 10 mg, which is approximately 5.3 mg/m^2 . The actual administered dose will depend on the subject's BSA and available capsule sizes ([Table 4b](#)). Because veledimex is an PO agent and is supplied in a fixed capsule size (5 mg and 20 mg), the actual administered dose is based on a subject's BSA and is bound by the rounding constraints set by 5 mg. The Sponsor developed a BSA-adjusted dosing algorithm designed to enable dosing within 25% of the target dose in mg/m^2 .

If a subject's BSA would expose the subject to $< 75\%$ or $> 125\%$ of the target assigned dose, the actual administered dose will be modified to ensure that the target dose in mg/m^2 is achieved. Minimum BSA restrictions for enrollment must be met in order for a subject to be appropriately dosed. Potential subjects whose BSAs do not have a correlated administered dose may be enrolled at the discretion of the Investigator and the Medical Monitor but will not be considered in the assessment of the recommended Phase II pediatric dose. Dosing of these subjects can only commence once the cohort has been reviewed by the SRC and determined that the dosing at the specified level (10 mg or 20 mg) is appropriate for escalation or as the recommended Phase II pediatric dose. These subjects will be analyzed separately.

The dosing table ([Table 4b](#)) illustrates this algorithm and captures the BSA adjusted-actual administered dose that subjects would receive at assigned dose levels based on a minimum capsule size of 5 mg.

Table 4b: Veledimex Dosing Table

Cohort	Target Dose (mg)	Min BSA (m ²)	Min BSA Target Dose (mg)	Percentage of Expected Dose (%)	Max BSA (m ²)	Max BSA Target Dose (mg)	Percentage of Expected Dose (%)	Actual Dose ^a (mg)
10 mg	5.3	0.5	10	189	0.75	6.7	126	5 ^b
10 mg	5.3	0.76	6.6	124	1.26	4.0	75	5
10 mg	5.3	1.27	3.9	74	1.5	3.3	63	5
10 mg	5.3	1.27	7.9	149%	1.5	6.7	126%	10 mg ^b
10 mg	5.3	1.51	6.6	125%	2.53	4.0	75%	10 mg
Cohort	Target Dose (mg)	Min BSA (m ²)	Min BSA Target Dose (mg)	Percentage of Expected Dose (%)	Max BSA (m ²)	Max BSA Target Dose (mg)	Percentage of Expected Dose (%)	Actual Dose ^a (mg)
20 mg	10.6	0.5	10	94%	0.63	7.9	75%	5 mg
20 mg	10.6	0.64	7.8	74%	0.75	6.7	63%	5 mg
20 mg	10.6	0.64	15.6	147%	0.75	13.3	126%	10 mg ^b
20 mg	10.6	0.76	13.2	124%	1.25	8.0	75%	10 mg
20 mg	10.6	1.26	11.9	112%	1.87	8.0	75%	15 mg
20 mg	10.6	1.88	10.6	100%	2.53	7.9	75%	20 mg

^a The actual dose is \pm 25% of the target dose.

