^b Subjects in this BSA range may be dosed at the discretion of the Investigator and the Medical Monitor

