### **13.2.2. Veledimex Exposure**

The number and percentage of subjects exposed to the veledimex study drug will be provided by treatment arm and the dose cohort, for the OSP.

Listings of treatment compliance and modification of study drug veledimex will be provided by the treatment arm, dose cohort, and subject ID for the OSP.

Veledimex study drug exposure will be summarized by subject ID for:

- Duration of exposure
  - In days, defined as last dose date – first dose date + 1
- Cumulative dose
  - Actual cumulative dose (mg), defined as the sum of all doses taken during the treatment period.
  - Expected cumulative dose (mg), defined as sum of all doses assigned during the treatment period.
- Dose intensity
  - Actual dose intensity (mg/day), defined as the actual cumulative dose (mg) divided by the duration of exposure (days).
  - Expected dose intensity (mg/day), defined as the expected cumulative dose (mg) divided by the duration of exposure (days).

- BSA-adjusted dosing
  - defined as the actual administered dose divided by body surface area (BSA).
  - BSA-adjusted dosing <75%, 75%-125%, and >125% will be categorized for summary.

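### The SAP does not keep children outside the BSA limits apart: its ESP omits BSA conformance, and its AE counts use all dosed subjects by dose cohort

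*SAP*

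**What the plan says.** **Protocol, enrollment and dosing.** Section 7.1, before Table 4b, states: "Potential subjects whose BSAs do not have a correlated administered dose may be enrolled at the discretion of the Investigator and the Medical Monitor". It then bars them from the assessment of the recommended Phase II dose, allows dosing only after the SRC has reviewed the cohort, and ends: "These subjects will be analyzed separately". The synopsis says the same. Footnote b of Table 4b marks three rows: "Subjects in this BSA range may be dosed at the discretion of the Investigator and the Medical Monitor".

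**Protocol, populations.** The synopsis, section 14 and section 16.1 all make BSA conformance a condition of the ESP. The recommended dose is determined from the ESP (section 7.5).

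**SAP, populations.** Section 5.2 defines the OSP as everyone given any study drug and says: "The data analysis for Adverse Events or other Safety variables will be performed on the OSP". Section 5.3 defines the ESP as subjects given Ad-RTS-hIL-12 and at least one cohort-specific veledimex dose, without a major deviation that confounds the key efficacy endpoints. It does not mention BSA.

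**SAP, outputs.** Section 7.1 sets the default: "data will be tabulated by arm and dose cohort, and overall according to the defined population". Section 11 summarizes DLT counts and proportions by arm and dose cohort on the ESP, if applicable. Section 13.1 presents treatment-emergent AEs by arm and dose cohort on the OSP. BSA enters only in section 13.2.2, on exposure: "BSA-adjusted dosing <75%, 75%-125%, and >125% will be categorized for summary".

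**The concern.** The primary endpoint in both documents is the AE rate and the occurrence of DLTs, analyzed by cohort. The protocol uses two devices to stop off-target children from blurring a cohort's result: a separate analysis, and an ESP limited to conformant subjects. A programmer working from the SAP would apply neither, because neither is written there.

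The departure is also undeclared. Protocol section 16 says deviations from its analyses will be indicated in the statistical plan, and SAP 6.1, which lists changes, does not include this one. SAP 7 classes any analysis designed after database lock as post hoc, so a separate analysis added later would lose its prespecified standing.

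With three to six subjects per escalation cohort, one child can visibly change a proportion.

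**Working it through.** **1. Reproduce Table 4b.** Percent of target = 100 x (actual dose / BSA) / target, with targets of 5.3 mg/m2 (10 mg cohort) and 10.6 mg/m2 (20 mg cohort). The first two footnote-b rows contain "0.5 10 189 0.75 6.7 126" and "1.27 7.9 149% 1.5 6.7 126": minimum BSA, dose per m2 there and percent of target, then the same for maximum BSA.

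| Cohort | Actual dose | BSA (m2) | mg/m2 | Computed % | Printed % |
|---|---|---|---|---|---|
| 10 mg, footnote b | 5 mg | 0.50 to 0.75 | 10.0 to 6.67 | 188.7 to 125.8 | 189 to 126 |
| 10 mg, footnote b | 10 mg | 1.27 to 1.50 | 7.87 to 6.67 | 148.6 to 125.8 | 149 to 126 |
| 20 mg, footnote b | 10 mg | 0.64 to 0.75 | 15.62 to 13.33 | 147.4 to 125.8 | 147 to 126 |
| 10 mg, no footnote | 5 mg | 1.27 to 1.50 | 3.94 to 3.33 | 74.3 to 62.9 | 74 to 63 |
| 20 mg, no footnote | 5 mg | 0.64 to 0.75 | 7.81 to 6.67 | 73.7 to 62.9 | 74 to 63 |

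All eleven rows of the table agree with the printed figures to within one percentage point. The three expressly discretionary rows are all above target. Two further rows lie below 75% and carry no footnote.

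**2. Same exposure, different column.** A child with BSA 0.5 m2 gets 5 mg in either cohort, which is 10.0 mg/m2. That is 188.7% of the 10 mg cohort's target and 94.3% of the 20 mg cohort's. Grouping by assigned cohort puts the same exposure in two columns, off-target in one and conformant in the other.

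**3. Trace a nonconformant child through the SAP.**
- OSP (5.2): included, since one dose of any study drug suffices.
- ESP (5.3): not excluded on BSA grounds. Receiving a cohort-specific dose is no substitute. Protocol 16.1 asks for that and for BSA conformance as well, and Table 4b assigns these children an actual dose within the cohort.
- The ESP's major-deviation clause is not a dependable route either, since SAP 8 says no subject leaves an analysis population because of a deviation.
- DLT proportions (11): can be counted, through the ESP.
- AE incidence (13.1): counted, through the OSP. That section ranks preferred terms by frequency and counts each subject once per term, so counts are intended.
- Exposure (13.2.2): placed in a BSA category that is not carried into the AE or DLT outputs.

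**4. Size of the effect (counts and rates are assumptions).** Expected rate = (n1 x p1 + n2 x p2) / (n1 + n2), with n1 = 6 conformant subjects at p1 = 20%.
- n2 = 1, p2 = 40%: (1.2 + 0.4)/7 = 22.9%.
- n2 = 3, p2 = 40%: (1.2 + 1.2)/9 = 26.7%.
- n2 = 1, p2 = 60%: (1.2 + 0.6)/7 = 25.7%.
- n2 = 3, p2 = 60%: (1.2 + 1.8)/9 = 33.3%.
- p2 = 20%: no shift for any n2.
- n1 = 36 (6 plus an expansion of 30), n2 = 3, p2 = 40%: (7.2 + 1.2)/39 = 21.5%.

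As observed counts, 1 of 6 (16.7%) becomes 2 of 7 (28.6%) if one added nonconformant child has the event.

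**The case against.** Much of the other side's case stands.

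- **Most safety outputs are listings.** SAP 6.1 avoids summaries of very small samples. Laboratory values, vital signs, ECG and performance status are by-subject listings or summaries (13.4 to 13.8), and section 13.1 also speaks of listings. A listing averages nobody into a rate. The point is therefore confined to AE incidence counts and DLT proportions.
- **The protocol's own safety text has the same gap.** The synopsis and section 16.4.2 tabulate safety by arm and dose cohort with no BSA split. It would be wrong to infer that the SAP alone departs from a complete protocol analysis. The missing ESP condition, however, is the SAP's own omission.
- **The group may be empty.** Exclusion criterion 3 bars subjects below 75% or above 125% of target, while section 7.1 and footnote b admit some at discretion. While the discretionary text stands, an analysis rule is needed.
- **The dose decision.** A reader might infer that the recommended Phase II dose would be contaminated. The protocol does not support that: these children are not considered for it and are dosed only after SRC review of the cohort. No formal 10 versus 20 mg comparison is planned either.
- **Direction.** A reader might also infer a bias toward higher toxicity in every column. The footnoted rows are all above target, but Table 4b also has rows at 63-74%, and SAP 13.2.2 provides for a below-75% category. Nearness to the 20 mg target holds only at the smallest BSA: the 5 mg row falls from 94% to 63% of 10.6 mg/m2 as BSA rises to 0.75 m2.
- **Linkage.** The exposure categories could be joined to AE listings by subject ID. That makes a later separation possible but does not prespecify it.

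**Conclusion.** The point holds as a gap between the SAP and two protocol rules, bearing on the primary endpoint. The clearer defect is the SAP 5.3 ESP, which drops BSA conformance and so leaves DLT proportions open to children the protocol excludes from that population. The second is that AE incidence by cohort uses the whole OSP with no separate report, a gap the protocol's statistical text shares.

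The off-target range for expressly discretionary children is certain, as it follows from Table 4b: 126-189% of target in the 10 mg cohort and 126-147% in the 20 mg cohort. The effect on any rate is not known. It needs at least one such child to be enrolled and a different event rate in that group. Under the assumed rates of 20% and 40% it is about 3 to 7 percentage points on six conformant subjects, and about 1.5 points when three are added to 36. These are illustrations, not predictions.

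**What to change.** 1. In SAP 5.3, restore BSA conformance as a condition of the ESP, so that the DLT proportions in section 11 use conformant subjects, as in protocol 16.1.
2. Define one BSA-conformance flag, and add it and the actual mg/m2 dose to the AE and DLT listings.
3. Wherever section 13.1 counts AE incidence by cohort, report nonconformant OSP subjects in their own column or listing, with an all-OSP total alongside so that no child's safety data are hidden.
4. Record the change in SAP 6.1, and add a matching sentence to protocol 16.4.2 at the next amendment.
5. Reconcile exclusion criterion 3 with the discretionary-enrollment text and footnote b. They contradict each other, and the analysis rule should follow whichever reading is settled.

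The cost is a flag and some additional table-shell columns or listings. SAP 13.2.2 already derives dose per BSA and its categories, so no new data are needed. The drawback is that separate columns may hold very few subjects; a flagged listing would then suffice, in keeping with SAP 6.1.
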